## 4. STATISTICAL METHODS

### 4.1. Sample Size Justification

A sample size of approximately 100 patients who receive two doses of FX006 is considered a reasonable sample size in order to assess the safety profile of repeat administration of FX006. No formal power and sample size calculations have been made as the analysis of the efficacy data collected from this study will be considered exploratory and hypothesis-generating for future multiple dose studies of FX006. In order to ensure at least 100 patients who receive two doses of FX006 are enrolled and followed for 52 weeks, approximately 200 patients will be enrolled based on an estimate that approximately 66% of patients enrolled will be eligible to receive a second dose of FX006 and approximately 75% of patients who receive a second dose will complete the study through Week 52.

### 4.2. General Statistical Methods and Data Handling

#### 4.2.1. General Methods

All output will be incorporated into Portable Document Format (PDF) or Word files, sorted and labeled according to the International Conference on Harmonisation (ICH) recommendations, and formatted to the appropriate page size(s).

A list of tables, figures and listings to be generated, as well as mock shells, are provided in a separate document.

Tabulations will be produced for appropriate demographic, baseline, efficacy and safety parameters. Each table will present all patients combined, regardless of number of doses, unless otherwise specified.

For categorical variables, summary tabulations of the number and percentage within each category (with a category for missing data) of the parameter will be presented.

For continuous variables, the number of non-missing values (n), the mean, median, standard deviation (SD), confidence intervals (CI), minimum and maximum will be presented. Additional statistics may be presented for certain endpoints as described in the sections below.

Time to event data will be summarized using Kaplan-Meier Methodology using 25th, 50th (median), and 75th percentiles with associated 2-sided 95% confidence intervals, as well as percent of censored observations.

If performed, all statistical tests will be two-sided and a difference resulting in a p-value of less than or equal to 0.05 will be described as statistically significant and potentially informative.

All collected data will be presented in patient listings.

The sections below describe the intended analysis of the endpoints. Additional sensitivity analysis may be employed in the event of any unforeseen data anomalies or data issues not known at the time of writing this analysis plan.

#### **4.2.2. Computing Environment**

All statistical analyses will be performed using SAS® Software (Version 9.4) or higher, unless otherwise noted. Adverse events will be coded using Medical Dictionary for Regulatory Activities (MedDRA) version 19.1 Concomitant medications will be coded using World Health Organization (WHO) Drug (March 2014 edition).

#### **4.2.3. Methods of Pooling Data**

Not applicable to the present study.

#### **4.2.4. Adjustments for Covariates**

The exploratory continuous endpoints will include baseline score and study site as covariates. Other covariates may be explored.

#### **4.2.5. Multiple Comparisons/Multiplicity**

Since these are exploratory analyses, there will be no adjustment for multiple endpoints.

#### **4.2.6. Subpopulations**

No pre-planned subpopulations are identified for this study. Subgroup tables and figures may be completed that are not identified in the list of planned tables and figures if needed to further explain results.

#### **4.2.7. Discontinuations and Loss to Follow-up**

Each treated patient in this study will receive an initial injection of FX006 and then be reevaluated starting at Week 12 for eligibility to receive a second injection. Therefore, discontinuation from treatment is not applicable. Whether or not patients receive the entire contents of study drug injection will be considered in the study drug exposure analyses.

Each patient may discontinue from the study for further assessments and study visits. Data collected from discontinued patients will be included in the CSR. Patients who discontinue from the study may be replaced at the discretion of the sponsor.

#### **4.2.8. Missing, Unused, and Spurious Data**

For WOMAC, the rules as described in the WOMAC user guide (Bellamy 2011) will be used. Specifically, if at least 2 pain, both stiffness, or at least 4 function items are missing, the patient's response will be regarded as invalid and the score for that given subscale as well as the total score will be left missing. If no more than 1 pain, 1 stiffness, and less than 4 function items are missing, the missing value in a given subscale will be imputed using the average of all items in the given subscale. Imputed WOMAC scores will be flagged in the data listings.

---

 Copyright 2015, SAS Institute Inc. SAS and all other SAS Institute Inc. product or service names are registered trademarks or trademarks of SAS Institute Inc., Cary, NC, USA.

For the KOOS QOL subscale, the rules as described in KOOS Scoring 2012 (<http://www.koos.nu/>) will be used. Specifically, the score is only calculated if at least 2 items are non-missing. Otherwise the score will be set to missing.

For calculating weekly mean steps per day using Fitbit data, patients need to have at least 3 of 7 daily values in a given week to provide a robust assessment of activity. The denominator used for calculating means will be the total number of days in which steps per day is non-missing.

To be included in the GPAQ analyses, there must be a valid response for at least one domain and no invalid responses for any domains.

Other than for the WOMAC and KOOS QOL, missing data will not be imputed and will be analyzed "as observed".

#### 4.2.9. Visit Windows

All data listings that contain an evaluation date will contain a relative study day (Rel Day Dose 1). Pre-treatment and post-treatment study days are numbered relative to the day of the first dose of study treatment, which is designated as Day 1. The preceding day is Day -1, the day before that is Day -2, etc. Listings will also contain a study day (Rel Day Dose 2) relative to the second dose of study treatment, which is designated as Day 1. For patients that do not receive a second dose, Rel Day Dose 2 will be "NA". For Rel Day Dose 2, preceding days (e.g., Day -1, -2) will not be derived or presented. In other words, if the date is prior to Dose 2, only Rel Day Dose 1 will be presented. If the date is after Dose 2, then both Rel Day Dose 1 and Rel Day Dose 2 will be presented.

##### Steps per Day (Fitbit) data windowing:

The visit windows to be used for computing steps per day are provided in [Table 2](#). Observations collected in these windows will be averaged and presented according to the nominal visit label for that window.

**Table 2      Evaluation Intervals for the Data Points to be Included in the Table**

Visit	Relative Day Interval for Analysis
Baseline	Day -7 to Day -1
Week 1	Day 1 to Day 7
Week 2	Day 8 to Day 14
Week 3	Day 15 to Day 21
Week 4	Day 22 to Day 28
Week 5	Day 29 to Day 35
Week 6	Day 36 to Day 42
Week 7	Day 43 to Day 49
Week 8	Day 50 to Day 56
Week 9	Day 57 to Day 63
Week 10	Day 64 to Day 70
Week 11	Day 71 to Day 77
Week 12	Day 78 to Day 84

**Unscheduled visit windowing:**

If a patient receives their second dose of study medication at an unscheduled visit that is not  $>3$  weeks after Week 24, the dosing information and all other data collected at that visit will be mapped to the closest nominal visit, based on Rel Day Dose 1, even if data is already available in that visit. All data collected at the time of the second dose will be used for analysis. If data is available in the nominal visit, but was not collected at the unscheduled visit associated with the second dose, the data from the nominal visit will be used. If a patient receives their second dose at an unscheduled visit that is  $> 3$  weeks past Week 24, data from that unscheduled visit will not be used for time to second dose analyses or exploratory efficacy analyses involving two-dose patients.

Data collected at unscheduled visits that are not associated with the second dose will be mapped to the closest scheduled visit, but only if that data is not already available in that visit. Otherwise data will be summarized and presented according to the nominal visit as recorded on the Case Report Form (CRF).

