## **2. STUDY DESIGN**

### **2.1. Synopsis of Study Design**

This study is an open-label, repeat administration design of 32 mg FX006. The study will be conducted in male and female patients  $\geq$  40 years of age with symptomatic OA of the knee.

Eligible patients will be offered participation to receive an initial IA injection of FX006 administered to the index knee at Day 1.

Patients who receive an initial injection of FX006 will return at Weeks 4 and 8 before being evaluated at 12, 16, 20 and 24 weeks following the initial administration of FX006 for repeat administration. At the first visit where the patient has been determined to meet repeat administration eligibility criteria, the patient will be eligible to receive a second IA injection of FX006 administered to the index knee.

Patients who are eligible to receive a second injection will be evaluated for a total of 52 weeks post initial injection at: Weeks 4, 8, 12, 16, 20, 24, 28, 32, 36, 40, 44, 48 and 52, regardless of the visit at which they receive their second injection.

Patients that do not benefit from the initial treatment as determined by evaluation at Week 12 will complete the study at the Week 12 follow-up visit. These patients will be evaluated for a total of 12 weeks post initial injection at: Weeks 4, 8, 12.

Patients who are not eligible for a second injection of FX006 after evaluation at Weeks 12, 16, 20, and 24 will complete the study at the Week 24 follow-up visit. These patients will be evaluated for a total of 24 weeks post initial injection at: Weeks 4, 8, 12, 16, 20 and 24.

Refer to [Appendix B](#) for the study flow chart.

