#### **4.7. Demographic and Baseline Characteristics**

Demographics and baseline characteristics will be summarized and presented for the SP for patients receiving only one dose, patients receiving two doses, and all patients combined. Age, height, weight, and body mass index (BMI) will be summarized using descriptive statistics (number of patients, mean, standard deviation, median, minimum, and maximum). Age will be calculated as the years between date of birth and date of informed consent, and will be rounded down to the nearest year. The number and percentage of patients in each gender, ethnicity and race category will also be presented. Additionally, for two-dose patients only, demographic and baseline characteristic data will be presented separately based on the time at which the second dose was administered. These statistics will be presented for the following groups. Each group will be displayed as a different column in the same table, in this order:

1. Patients receiving the second dose at Week 12
2. Patients receiving the second dose at Week 16
3. Patients receiving the second dose at Week 20
4. Patients receiving the second dose at Week 24
5. Patients Receiving the Second Dose after Week 24

OA background characteristic data and index knee characteristic data as collected on the CRF will also be tabulated for the SP for all patients combined. Time from primary diagnosis of OA in the index knee to Day 1 of the study in years (dose date – date of diagnosis + 1)/365.25, will be computed and presented descriptively. Additionally, for two-dose patients only, OA background characteristic data and index knee characteristic data will be presented separately based on the time at which the second dose was administered. These statistics will be presented

for the following groups. Each group will be displayed as a different column in the same table, in this order:

1. Patients receiving the second dose at Week 12
2. Patients receiving the second dose at Week 16
3. Patients receiving the second dose at Week 20
4. Patients receiving the second dose at Week 24
5. Patients Receiving the Second Dose after Week 24

For all time to diagnosis calculations, if only month and year of initial diagnosis is available, day will be imputed as 1 for calculations. If month and day are missing, the time from primary diagnosis will be computed as year of administration of study treatment minus year of diagnosis. If year is missing, time from diagnosis will not be computed.

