- Any index-knee related TEAE by relationship
- Any TEAE related to injection procedure

Separate tabulations will be produced for each of following categories:

- All TEAEs by SOC and PT
- All SAEs by SOC and PT
- All TEAEs related to study drug by SOC and PT
- All TEAEs related to injection procedure by SOC and PT
- All TEAEs by maximum severity by SOC and PT
- All TEAEs leading to study discontinuation
- All TEAEs leading to death
- All index-knee related TEAEs by SOC and PT
- All index-knee related TEAEs related to study drug by SOC and PT
- All index-knee related TEAEs by maximum severity by SOC and PT

Summary tables and the tabulation of All TEAEs by SOC and PT will be presented for the following patient groups and time periods, with a separate table for each patient group:

1. Patients receiving only one dose
  - a. First dose to Week 12
  - b. First dose to Week 24 (end of study)
2. Patients receiving the second dose at Week 12
  - a. First dose to Week 12
  - b. Week 12 to Week 24
  - c. Week 12 to Week 52
3. Patients receiving the second dose at Week 16
  - a. First dose to Week 16
  - b. Week 16 to Week 32
  - c. Week 16 to Week 52
4. Patients receiving the second dose at Week 20
  - a. First dose to Week 20
  - b. Week 20 to Week 40
  - c. Week 20 to Week 52
5. Patients receiving the second dose at Week 24
  - a. First dose to Week 24
  - b. Week 24 to Week 48
  - c. Week 24 to Week 52

Summary tables and all tabulations will be presented for the following time periods for patients receiving two doses only (same table):

1. Baseline to Week 52
2. Baseline to Week 12
3. Second dose to 12 weeks after second dose

Date and time of onset of TEAE will be used to assign the time periods.

In the summary table for "Any TEAE by SOC and PT", an additional row with the number of events observed will be presented. A patient will be counted once for the number of patients if they have multiple events. The total number of events will be the absolute number of events observed, and a patient will be counted more than once for the event totals if they have multiple events.

In these tabulations, related is defined as any TEAE deemed possibly, probably or definitely related to study drug by the investigator. If relationship is missing, it will be imputed as related.

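### SAP 4.2.9 maps unscheduled second doses given 15 to 21 days after Week 24 to Week 28, where the by-timing efficacy and AE tables have no group and the pre-dose record displaces the real Week 28 visit

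*SAP*

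**What the plan says.** **The mapping rule.** SAP 4.2.9 (unscheduled visit windowing) covers a second dose at an unscheduled visit that is not more than 3 "weeks after Week 24, the dosing information and all other data collected at that visit"; these "will be mapped to the closest nominal visit, based on Rel Day Dose 1, even if data is already available in that visit". It continues: "All data collected at the time of the second dose will be used for analysis". The nominal visit's own value survives only where an item "was not collected at the unscheduled visit associated with the second dose, the data from the nominal visit will be used". Where no second dose is involved, the order is reversed: an unscheduled value fills a visit only if that visit is empty.

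**Beyond the limit.** For a second dose more than 3 "weeks past Week 24, data from that unscheduled visit will not be used for time to second dose analyses", nor for exploratory efficacy analyses of two-dose patients. Safety analyses are not mentioned.

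**The visit grid.** For patients eligible for repeat dosing, SAP 2.1 sets this follow-up schedule: "Weeks 4, 8, 12, 16, 20, 24, 28, 32, 36, 40, 44, 48 and 52, regardless of the visit at which they receive their second" dose. Week 28 is therefore a nominal visit, and 4.2.9 does not restrict mapping to the four visits at which a second dose is planned (Weeks 12, 16, 20 and 24; Protocol Table 1, footnote 16).

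**The timing groups.** SAP 4.7 lists a fifth column, "Patients Receiving the Second Dose after Week 24", for both the demographic and the OA-background tables. In 4.9.1.1 (WOMAC descriptive and MMRM), 4.9.1.3 (responders), 4.9.1.4 with Table 3 (AUE) and 4.10.1 (AEs), the last second-dose group is "Patients receiving the second dose at Week 24". KOOS follows 4.9.1.1.

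**The concern.** The SAP chooses to keep second doses given up to 3 weeks late, and 4.7 shows that it expects some second doses after Week 24. If a kept dose is labelled Week 28, its patient has no column in the by-timing efficacy and AE tables, and a programmer must improvise. Timing of the second dose is the main breakdown the SAP uses for both safety and efficacy, so the gap should be closed before the tables are run.

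The second issue is which record is analysed. Anything collected at the second-dose visit before injection describes the end of the first-dose period. Under the rule it takes the place of a Week 28 assessment made after dose 2, for every item collected at both visits.

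**Working it through.** **Inputs.** The first dose is Day 1 (SAP 4.2.9). Visits are four-weekly (SAP 2.1). The visit allowance is ±7 days (Protocol Table 1, footnote 2). The late limit is 3 weeks, or 21 days (SAP 4.2.9).

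**The plan's own figures.** For a second dose at week w, Table 3 uses a second-dose interval from w+4 to 2w. This gives 16–24, 20–32, 24–40 and 28–48 for w = 12, 16, 20 and 24, all as printed. For w = 28 it gives 32–56, which runs past Week 52. Table 3 therefore cannot take a Week 28 dose on its own pattern.

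**Which days map to Week 28.** Week w falls on Day 7w+1.

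- Week 24 = 7×24+1 = Day 169; Week 28 = 7×28+1 = Day 197.
- Midpoint = (169+197)/2 = Day 183. It is 14 days from each visit, and no tie-break is given. The same gap exists at other midpoints, such as Day 155 between Weeks 20 and 24.
- Late limit = 169+21 = Day 190.
- Days 170–182 are nearer Week 24. Days 184–190 (15–21 days late, 7 of the 21 allowed days) are nearer Week 28.

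If Week w is instead taken as Day 7w, as the ends of the Table 2 intervals suggest, every day moves back by one and the distances are unchanged.

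**The displaced record.** An on-schedule Week 28 visit falls 197−190 = 7 to 197−184 = 13 days after dose 2. Allowing ±7 days, the range is 190−190 = 0 to 204−184 = 20 days.

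**Timing error under each label**, for a dose on Day 184 to Day 190:

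| Label given to dose 2 | Error in dose time | Visit taken as 4 weeks after | Visit taken as 12 weeks after |
|---|---|---|---|
| Week 28 (current rule) | 13 to 7 days = 1.9 to 1.0 weeks late | Week 32 (Day 225): 41 to 35 days = 5.9 to 5.0 weeks | Week 40 (Day 281): 97 to 91 days = 13.9 to 13.0 weeks |
| Week 24 | 15 to 21 days = 2.1 to 3.0 weeks early | Week 28 (Day 197): 13 to 7 days = 1.9 to 1.0 weeks | Week 36 (Day 253): 69 to 63 days = 9.9 to 9.0 weeks |

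**Where these patients are and are not counted.**

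- No column: the by-timing second-dose groups in 4.9.1.1, 4.9.1.3, Table 3, KOOS and 4.10.1.
- Counted: the paired and Week 4/8/12 two-dose analyses (4.9.1.2), subject to data at the required time points; the AUE column for all two-dose patients; the pooled two-dose AE tables (4.10.1); X-ray results for all two-dose patients combined (4.10.5); and the two late-dose columns in 4.7.
- Counted until dose 2: the column for all patients after the first dose (4.9.1.1, 4.9.1.3). Under the rule this column can acquire a Week 28 level filled only by patients dosed late, in a model with an unstructured covariance.
- Patients dosed more than 3 weeks late remain in the safety analyses, but they too have no by-timing AE group.

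**The case against.** The strongest reply is that only a breakdown column is missing. In 4.10.1 the summary and all AE tabulations are produced for two-dose patients pooled, with periods set by the onset date and time of the event. The by-timing AE tables cover only the summary and TEAEs by SOC and PT. Deaths, SAEs and AEs leading to discontinuation are listed for all patients. This stands. A reader might infer that two-dose patients disappear from the primary safety evaluation; the documents do not support that.

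The mapping also has a sound side. For Days 184–190, Week 28 really is the nearer visit, and the Week 24 label is further out. This stands too, and it rules out the tempting repair of relabelling these doses as Week 24. That repair would also overwrite the real Week 24 record. The drafters may have meant Week 24, because the 21-day limit falls on Day 190, when the Week 28 window opens, but the SAP does not say so.

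The displacement is limited. In the pooled analyses the pre-dose record properly serves as the dose-2 baseline under 4.2.10, and a visit 7 to 13 days after dose 2 is not one of the 4-, 8- or 12-week points. While these patients have no by-timing column, their Week 28 row is not shown there either. Nominal values are kept for items not collected at the dosing visit, and all collected data are listed. A reader might infer that Week 28 data are lost; what is at issue is the choice of analysis record.

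A reader might also infer that the time-to-second-dose summary is biased. SAP 4.8 does not say whether it uses the mapped visit or the dose date. If it uses the mapped visit, each affected time is overstated by 1.0 to 1.9 weeks. The summary reports the 25th, 50th and 75th percentiles, however, and a late tail would reach the 75th only if about a quarter of two-dose patients were this late.

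**Conclusion.** The point holds as a gap between the mapping rule and the group lists. Unscheduled second doses 15 to 21 days after Week 24 are sent to a visit for which the by-timing efficacy and AE tables have no second-dose group. The pre-dose record is also preferred to a post-dose-2 record at that visit. Patients dosed later still lack a by-timing AE group as well.

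The gap does not reach every second dose after Week 24: unscheduled doses 1 to 13 days late map to Week 24 and have a group. The pooled two-dose results remain available.

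The documents do not say how many patients are affected. Since dosing this late is off-schedule, the number is probably small, and no change of conclusion can be shown. The result assumes a literal reading of the nearest-visit rule, Week 24 on Day 169 (or 168), and an on-schedule Week 28 visit for the 7-to-13-day figure. It is worth correcting because the SAP already foresees these patients and the repair is cheap.

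**What to change.** 1. **Groups.** Add the after-Week-24 group of 4.7 to the by-timing AE tables in 4.10.1, with two periods: first dose to second dose, and second dose to Week 52. Add it to the WOMAC descriptive table (4.9.1.1) and the responder table (4.9.1.3) for patients whose data are retained. Define its membership once, including the tie at Day 183. For Table 3, state that the comparable period would run past Week 52, so no such column is given.
2. **Record.** Amend 4.2.9 so that a second-dose record from an unscheduled visit after Week 24 serves as the dose-2 baseline, in line with 4.2.10, and does not overwrite the genuine Week 28 visit.
3. **Timing.** Use the actual dose date for time to second dose, and Rel Day Dose 2, already derived for the listings, to place the time points after dose 2.

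The cost is a few sentences of SAP text, one small extra group whose summaries may rest on very few patients, and minor programming. These are changes to analysis text only; nothing is proposed about when a second dose is given.

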##### **7.4.3.1. Repeat Administration Inclusion Criteria**

To be eligible to receive a repeat administration, patients must fulfill the following criteria:

1. Benefit from the initial dose of FX006 in the opinion of both the patient and the Investigator
2. No major safety concerns during the initial dose period as assessed by the Investigator
3. Clinically indicated to receive a second dose of FX006 in the opinion of both the patient and the Investigator
4. WOMAC A total sum score of  $\geq 6$  or a clinical rationale as to why a second dose is indicated
5. Compliant with study procedures and visit schedules through at least Week 12 and the willingness and ability to continue to comply through Week 52
6. Willingness to abstain from use of protocol-restricted medications during the study

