**4.2.10.      Baseline Definitions**

Baseline for the first dose is the baseline/Day 1 assessment prior to administration of the first dose of study treatment. If the baseline result is missing, the last non-missing result prior to administration of study treatment may be used from the Screening period.

Baseline for the second dose of study treatment is defined as the last data collected prior to the second dose of study treatment administration. This is the same study visit, as long as the data are collected prior to the second dose.

Where noted in this SAP, change from baseline for efficacy analyses are also performed where baseline for the second dose is defined as the baseline/Day 1 assessment prior to administration of the first dose of study treatment.

Additional baselines may be defined to explore efficacy endpoints comparing the first dose and the second dose of study treatment administration. All new baseline definitions will be fully specified and documented in an interim SAP (iSAP) and in the final CSR.

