#### 4.9.1.2. Change from baseline, patients receiving two doses

##### Change from Baseline to Week 12

A within patient analysis will be completed for patients who receive two doses of FX006. Change in WOMAC A, WOMAC B, WOMAC C and WOMAC total from first dose (Day 1) to Week 12 will be compared to change in WOMAC from second dose to 12 weeks after the second dose using a paired t-test.

The paired t-test will be completed by using the SAS/STAT® PROC MIXED procedure. Using the PROC MIXED procedure allows for multivariate modelling. Model covariates are study site, baseline WOMAC score, and potentially other covariates. Baseline WOMAC score for the first dose comes from the baseline visit. Baseline WOMAC score for the second dose comes from the second dose visit.

Descriptive statistics will include number of observations, unadjusted mean, standard deviation, median, minimum and maximum. Change from baseline LSM, SE and 95% CI from the mixed model will also be presented. The difference between the first dose (the control) and the second dose will be presented, and estimated via LSM from the analysis model along with 95% confidence intervals and associated 2-sided p-values. This model assumes that missing values are missing at random. Only patients that have data for both time points (i.e., change from Day 1 to Week 12 and change from the second dose to 12 weeks after the second dose) will be included in the model.

All patients who receive two doses of FX006 will be combined in the analysis and results will be displayed in the same table.

Sample SAS code that can be used to implement the analysis is provided below:

```
proc mixed data=<ADaM> method=type3;
  class subjID site arm;
  model chg = base site arm/ alpha=0.05 ddfm=kr outp=pred residual solution;
  random subjID;
  lsmeans arm / diff cl alpha=0.05;
  ods output diff=diff1 lsmeans=lsml;
run;
quit;
```

In the above code, "arm" refers to the first or second dose administered (coded as a 1 or 2).

The analysis above will also be performed to compare the changes in WOMAC A, WOMAC B, WOMAC C and WOMAC total from first dose (Day 1) to Week 12 to the changes from first dose (Day 1) to 12 weeks after the second dose.

#### Change from Baseline to Week 4, 8 and 12

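### An unscheduled second-dose visit can overwrite a valid on-schedule score, and where re-dosing was driven by the score this probably makes the first dose look worse

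*SAP*

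**What the plan says.** SAP 4.2.9 (unscheduled visit windowing) covers a second dose given at an unscheduled visit no more than 3 weeks after Week 24. Everything from that visit is "mapped to the closest nominal visit, based on Rel Day Dose 1, even if data is already available in that visit". It continues: "All data collected at the time of the second dose will be used for analysis". The on-schedule record survives only item by item, when something is available there "but was not collected at the unscheduled visit associated with the second dose, the data from the nominal visit will be used".

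Unscheduled visits without a second dose follow the opposite rule. Their data are "mapped to the closest scheduled visit, but only if that data is not already available in that visit".

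SAP 4.2.10 deals with the second-dose baseline separately: "Baseline for the second dose of study treatment is defined as the last data collected prior to the second dose of study treatment administration".

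In SAP 4.9.1.2, the change in WOMAC "from first dose (Day 1) to Week 12 will be compared to change in WOMAC from second dose to 12 weeks after the second dose" by a paired t-test fitted in PROC MIXED, with 95% confidence intervals and two-sided p-values.

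Protocol 7.4.3.1 (item 4) asks for a WOMAC A sum of at least 6 before re-dosing, "or a clinical rationale as to why a second dose is indicated". Other criteria apply as well.

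**The concern.** Suppose a patient attends Week 12 on Day 85 with a WOMAC A sum of 5, is not re-dosed, returns on Day 95 with a sum of 6 and is re-dosed. Day 95 is closest to Week 12. The Day 95 score becomes the Week 12 value, and the Day 85 score drops out of the summaries. No gap is being filled, because both scores exist. The rule keeps the one that can be linked to the outcome, since pain may have returned by then.

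The Week 12 value feeds:
- the paired comparison and the Week 4/8/12 display (SAP 4.9.1.2);
- the by-visit models (4.9.1.1);
- the Week 12 responder rate and curve (4.9.1.3);
- the Week 4 to 12 AUE (4.9.1.4);
- the corresponding KOOS analyses (4.9.2).

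SAP section 5 drops the one-dose versus two-dose comparisons, so the within-patient comparison of the two doses is the main formal efficacy contrast left. A replacement that raises first-dose pain scores tilts it towards the second dose.

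**Working it through.** The plan gives no figure for this rule, so there is none to reproduce. The steps below establish which visits are affected, the direction and the possible size.

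**1. Which days overwrite Week 12.** Take nominal day = 7 × week + 1, with the first dose on Day 1. Week 12 is then Day 85 and Week 16 is Day 113. The midpoint is (85 + 113)/2 = Day 99, a tie that the SAP does not resolve. A second dose on Days 86–98 (13 days) therefore maps back to Week 12. If Week 12 is counted as Day 84, the range moves one day earlier. Later off-schedule doses overwrite Week 16, 20 or 24 when they follow those visits, and leave Week 12 intact.

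**2. Smallest shift when the delay was score-driven.** WOMAC A has a maximum sum of 20 and is analysed as an item average of 0–4 (SAP 4.9.1), so average = sum/5. With all items answered, a sum of 5 or less is at most 1.0 and a sum of 6 or more is at least 1.2. The replacement is worse by at least 1.2 − 1.0 = 0.2.

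**3. Plausible mean shift d.** Pairs of on-schedule and re-dose scores were simulated with assumed mean sum 3–6, SD 3–4, correlation 0.6–0.9 and drift 0–1 sum point.

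| Selection | Mean shift, 0–4 scale |
|---|---|
| Below 6 on schedule, 6 or more at re-dose | 0.36 to 0.95 |
| Only the re-dose score is 6 or more | 0.05 to 0.52 |
| No selection on score | 0 to 0.20 |

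**4. Effect on the paired test.** The second-dose change does not move, because its baseline is the last pre-dose value under either rule. If a share f of the analysed pairs has an overwritten Week 12 score, the first-dose mean moves by f × d. In standard errors this is δ = f × d × √n / SD. The two-sided rejection rate when the doses are equal is Φ(−1.96 + δ) + Φ(−1.96 − δ).

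Here f, d, n and SD are all assumptions. The range for n is 140–180; the upper end is 0.90 × 200. The range for SD is 0.7–1.0. Example: f = 10%, d = 0.5, n = 140, SD = 0.7 gives a shift of 0.05, δ = 0.05 × √140 / 0.7 = 0.85 and a rejection rate of 13.5%. Over the ranges of n and SD:

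| f | d = 0.2 | d = 0.5 | d = 0.8 |
|---|---|---|---|
| 2% | 5.0–5.1% | 5.2–5.4% | 5.4–6.1% |
| 5% | 5.2–5.4% | 6.0–7.7% | 7.6–12.0% |
| 10% | 5.6–6.7% | 9.1–16.0% | 15.7–33.5% |

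At d = 0 there is no bias. At a negative d the sign reverses.

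**5. Responders.** With a baseline sum of 10, an on-schedule 5 is a 50% decrease and counts as a response. Replaced by 6, the decrease is 40% and the patient becomes a non-responder.

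**6. AUE.** By the trapezoidal rule with 4-week steps, the Week 4 to 12 area is 2·W4 + 4·W8 + 2·W12. Week 12 carries 2/8 = one quarter of the weight, so a quarter of any shift reaches the time-averaged AUE.

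**The case against.** **Direction.** A reader might infer that the rule always makes the first dose look worse. The documents do not support that. They do not say why off-schedule re-dosing occurred, and a patient not eligible at Week 12 is next evaluated at Week 16. A delay can have causes unrelated to the score, such as recent antibiotics or skin breakdown at the injection site (Protocol 7.4.3.2), and a clinical rationale can stand in for the score. The Week 12 sum may already have been 6 or more. KOOS is not a re-dosing criterion, so selection on it is indirect. All of this stands: the direction is near-certain only for score-driven delays.

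**Scope.** A reader might also infer that every off-schedule second dose replaces the Week 12 result. Only about 13 days do. Days 86–92 also lie inside the protocol's ±7-day visit window, so a score there has acceptable timing. That stands, but it does not explain why an earlier valid score should give way to it.

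**Proper replacement.** If the unscheduled dose comes before the nominal visit, the nominal score is post-dose-2 and should not count as first-dose data. In the AUE that runs up to the second dose, the dosing-visit score is a natural endpoint. Both points stand and limit the fix.

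**Loss of data.** The overwritten score is not lost altogether, because all collected data are listed (SAP 4.2.1).

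**Importance.** Efficacy is exploratory, with no multiplicity adjustment. The primary objective is safety, and TEAE periods are assigned by onset date and time (SAP 4.10.1), so the overwrite does not reach them. This lowers the severity but does not remove the point.

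**Conclusion.** The concern holds in limited form. The SAP prescribes the overwrite explicitly, applies the opposite rule to other unscheduled visits, and does not need it for the second-dose baseline. Nothing elsewhere keeps the on-schedule score in first-dose summaries, and SAP 4.9.5 leaves sensitivity analyses optional and post hoc.

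Week 12 is affected only by second doses on about Days 86–98; later off-schedule doses alter the Week 16, 20 or 24 by-visit results instead. For score-driven delays the first dose probably looks worse; otherwise the shift may be nil or reversed. At an assumed mean shift of 0.5, the effect on the paired test is negligible with about 2% of pairs affected and material from about 10%. Neither document gives the affected share, the shift or the paired SD, so no one of these rates can be taken as the expected one. Severity is modest.

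**What to change.** Amend SAP 4.2.9 to state that:

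- if the closest nominal visit was attended before the second dose, its score remains the value for that visit in first-dose, by-visit and responder analyses;
- the unscheduled pre-dose score is held as a separate record, used for the second-dose baseline, for dose timing and as the endpoint of the AUE from Week 4 to the second dose;
- that score fills the nominal visit only if the visit has no value from before the second dose;
- a nominal-visit score collected after the second dose is not used as first-dose data.

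Report how many scores the current rule would overwrite, by nominal visit, and show the paired comparison of 4.9.1.2 both ways. Grouping by week of second dose can stay as it is.

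The cost is a few sentences in the SAP, one extra analysis flag and one repeated analysis. No new data are needed.
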